As a result of inhibition of RTKs by TKI258, cellular functions are blocked, including activation of downstream-signaling molecules, cellular proliferation, and survival. In cultured human endothelial cells expressing VEGFR, TKI258 inhibits VEGF stimulated mitogenesis. In a FGF2 dependent model of angiogenesis, TKI258 potently inhibited neovascularization of Matrigel plugs in vivo with an average ED50 of 3 mg/kg. The effects on endothelial cells suggest that TKI258 may have potent antiangiogenic activity. Additionally, direct antiproliferative effects were observed in cell lines; those cells that expressed an RTK inhibited by TKI258 were most sensitive to the drug (MV4;11: an acute myeloid leukemia [AML] cell line driven by constitutively active FLT3; TF 1: a AML cell line driven by c-KIT; KMS11: a multiple myeloma line driven by an activating mutation in FGFR3; RT112 and RT4 bladder cancer cell lines overexpressing FGFR3; and the colon cancer cell line KM12L4a, driven by TPM3-TRKA translocation). Antitumor effects for this agent may therefore be conferred by antiangiogenesis, antistromal activity, and antiproliferative activity directed against tumor cells that directly express TKI258 targets.

The antitumor activity of TKI258 was evaluated in a variety of tumor xenograft models in athymic mice. In all models tested, TKI258 administered orally caused anti-tumor responses, ranging from growth inhibition and stasis to regression in tumor models driven by activating mutations of TKI258 targets. Furthermore, in a model of disseminated disease, colonization of breast cancer cells in the livers of mice from a subcutaneous (SC) xenograft primary was significantly reduced by oral treatment with TKI258. To demonstrate that direct inhibition of RTKs in tumors was a primary mechanism of xenograft growth inhibition by TKI258, tyrosine phosphorylation of VEGFR2, PDGFR β , FGFR3 and the downstream-signaling proteins AKT (also known as protein kinase B) and ERK (also known as MAPK) was shown to be inhibited following a single oral dose of TKI258. Inhibition was observed up to 24 hours (h) in some models. These results indicate that TKI258 may be useful in the treatment of disseminated disease and leukemia, as well as solid tumors and myeloma. The broad target profile of TKI258 is likely to contribute to its efficacy in many different types of tumor models by acting on endothelial cells and tumor cells.

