1.4 Pre-clinical studies

TKI258 was evaluated in a number of *in vitro* and *in vivo* nonclinical models to characterize its pharmacology, antitumor efficacy, pharmacokinetics, metabolism, and toxicology. TKI258 is an RTK inhibitor with potent antiangiogenic and antiproliferative activity. It targets type III, IV, and V RTKs, which include PDGFR^β, CSF 1R, KIT, FLT3, VEGFR, TrkA, RET and FGFRs. The biochemical and cell based potency against these receptors is in the nanomolar range. As a result of inhibition of target RTKs by TKI258, cellular functions are blocked, including activation of downstream-signaling molecules, cellular proliferation, and survival. Additionally, in vivo antitumor effects have been observed in a variety of nonclinical models representing solid and hematological cancers. The *in vivo* effects of TKI258 were shown to be a result of its dual mechanisms of action: antiangiogenesis and direct antitumor activity. Inhibition of angiogenesis (through inactivation of VEGFR, PDGFRB, and FGFR on stroma and endothelium) was demonstrated by a reduction in hemoglobin concentration in subcutaneous Matrigel plugs, as well as reduced microvessel density in tumor xenografts after administration of TKI258. Direct inhibition of RTK activation on tumor cells (PDGFRB, FLT3, and FGFR 1 & 3) was confirmed by a reduction in phosphorylation of these target RTKs, as well as signaling pathway components (ERK, STAT5, and AKT) in tumor xenografts (Chase et al. 2007). Target inhibition was observed for as long as 24 h after a single high dose of TKI258. A decrease in tumor cell proliferation and induction of apoptosis, in combination with the antiangiogenic effect of TKI258, resulted in significant antitumor efficacy. The target profile of TKI258 is likely to confer activity in many different types of solid and hematologic tumor models by acting on both endothelial cells and tumor cells. In all human tumor xenograft models tested, including colon, prostate, myeloma, AML, breast, and ovarian, TKI258 had anti-tumor effects on both small and large established tumor xenografts.

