5.0 STUDY TREATMENT(S)

5.1 TKI258 dose and schedule

Patients will receive a single daily oral dose of of TKI258 for 5 consecutive days, followed by a 2-days rest period. Following an initial 4-week cycle at a starting dose of 400 mg 5 days- on and 2 days off, TKI258 may be escalated to 500 mg/day 5 days-on/2 days off if no significant Grade3/4 AEs or laboratory abnormalities are observed. The dose of TKI258 is NOT individually adjusted by weight or body surface area. TKI258 should be ingested with sufficient amount of water at least 1 hour prior to a meal (breakfast) or at least 2 hours following a meal (breakfast). Alternatively, TKI258 may be taken with a. low-fat meal of \leq 500 calories with \leq 20 grams fat.

Treatment cycle

A cycle is arbitrary defined as 28 days (4 weeks) for the purposes of scheduling procedures and evaluations.

A complete treatment cycle is defined as 28 days or 4 weeks.

- TKI258 if given on days 1-5, 8-12, 15-19, 22-26 (5 days on/2 days off) of each cycle.
- The first administration of TKI258 defines Day 1 of the cycle. The last day of a complete cycle is Day 28.

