7.4 Evaluation during Treatment

On-study tests/visits that must occur within a defined time frame will have a standing window of allowance that is equal to +/- 3 days for any laboratory testing. If

screening lab tests take place less than 7 days prior to C1D1, laboratory testing will not be repeated.

7.4.1 Beginning on Cycle 1 Day 1 and continuing every 4 weeks thereafter, patients will undergo the following additional testing:

- History and physical exam
- Vital Signs (BP, pulse)
- Weight
- PS (ECOG)
- Assessment of concurrent medications
- Assessment of AEs
- PSA test
- Blood for Biomarker studies (Day 1 of Cycles 2 and 3 only)
- Serum chemistry must include: BUN, creatinine, total bilirubin, albumin, SGOT [AST], SGPT [ALT], GGT, LDH, amylase, lipase, alkaline phosphatase, fasting glucose, calcium, sodium, magnesium, phosphorus, and potassium

7.4.2 On Cycle 1, Days 12 and 26 and Cycle 2 Day 12 patients will undergo the following tests:

- CBC with differential/platelets
- Serum chemistry must include: BUN, creatinine, total bilirubin, albumin, SGOT [AST], SGPT [ALT], GGT, LDH, amylase, lipase, alkaline phosphatase, fasting glucose, calcium, sodium, magnesium, phosphorus, and potassium
- There will be a blood draw for a TKI258 trough concentration (Cycle 2 Day 12 Only) to evaluate the potential relationship of safety and efficacy in regards to steady state drug concentrations.

Note that the Day 26 of Cycle 1 visit could end up being scheduled on the same day as the Day 1 of Cycle 2 visit described above.

7.4.3 Beginning on Cycle 1 Day 1 and every 4 weeks for the first 8 weeks, and every 8 weeks thereafter, patients will undergo the following additional testing:

- Urine N-telopeptide
- Bone Alkaline Phosphatase

7.4.4 ECGs, cardiac enzymes, and MUGA/ECHO during therapy will be assessed as shown below in Table 7.1:

Table	7.1
-------	-----

Assessment	Cycle and Day	Time Point
12-lead ECG	Screening	Anytime
	Cycle 1, Day 1	3 sequential ECGs, separated
		by at least 5 to 10 minute
		intervals pre-dose
	Cycle 1, Day 1	1 ECG six hours post-dose
	Cycle 1, Day 26	1 ECG pre-dose
	Cycle 2, Day 26	1 ECG pre-dose
	Cycle 3, Day 26	1 ECG pre-dose
	Cycle 4+, Day 1	Anytime at the end of the
		previous cycle
	EOT	Anytime
Cardiac enzymes (troponin I	Screening	Anytime to coincide with
or B, CPK, and CPK-MB)		ECHO/MUGA
	Every 12 weeks while	To coincide with
	receiving therapy	ECHO/MUGA
	EOT	Anytime to coincide with
		ECHO/MUGA

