ECHO/MUGA	Screening	Anytime to coincide with
		cardiac enzymes
	Every 12 weeks while	To coincide with cardiac
	receiving therapy	enzymes
	ЕОТ	Anytime to coincide with
		cardiac enzymes.

7.4.5 A bone marrow biopsy and aspirate will be performed between 7 and 10 weeks (preferably at week 8) after beginning treatment. The specimens will be evaluated by pathology. A small portion of the bone marrow aspirate will be used for bone marker testing (to include bone marrow androgen levels).

7.4.6 Routine restaging scans and/or other disease assessment diagnostics will be performed every 8 weeks for the first 6 months and every three months thereafter. Such studies can be also be performed at the time of clinical disease progression (at the discretion of the study investigator).

7.5 Final Study Visit:

At the end of the study and within 4 weeks of study drug termination the following will be performed

- History and physical exam
- Vital Signs (BP, pulse)
- Weight

- Eastern Cooperative Oncology Group (ECOG) Performance Status
- Assessment of concurrent medications
- Adverse event evaluation
- Laboratory testing:
- CBC with differential/platelets
- Serum chemistry must include: BUN, creatinine, total bilirubin, albumin, SGOT [AST], SGPT [ALT], GGT, LDH, amylase, lipase, alkaline phosphatase, fasting glucose, calcium, sodium, magnesium, phosphorus, and potassium
- PSA test
- N-telopeptides in urine
- Correlative Studies (serum and bone marrow androgen testing, plus additional serum/plasma banking)
- Disease Status Assessment
- Chest X-ray
- Electrocardiogram (if not done in the past 6 weeks)
- CT or MRI scans of the pelvis and abdomen (if indicated)
- Bone scan (if indicated)
- Bone marrow biopsy and aspirate: The specimens will be evaluated by pathology. A small portion of the bone marrow aspirate will be used for bone marker testing.
- 7.6 Long-Term Follow Up

Patients will be followed a minimum of every 3 months by clinic visit (at M.D. Anderson or a local physician), telephone or e-mail correspondence to assess delayed toxicity and survival time.

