Data Analysis. If the data on the 40 patients yield a sample mean of 10 months (the targeted 25% improvement) based on total follow-up time 400 months (all 40 deaths observed) then the posterior of m would be IG(42.064, 408.512), which has mean 9.95 months and posterior 95% credible interval 7.33 - 13.4 months. Similarly, if 35 deaths are observed with 5 death times administratively censored and total follow-up 460 months at the final analysis then the posterior of m would be IG(37.064, 468.512),), which has mean 13 months and posterior 95% credible interval 9.39 - 17.95 months. Unadjusted survival time will be estimated using the method of Kaplan and Meier (27). The effects of the following four potential prognostic covariates on Prob(PSA response) will be estimated using logistic regression (28), and on survival time will be estimated using the Cox model or, if the proportional hazards assumption is not satisfied, using an appropriate time-to-event regression model chosen based on preliminary goodness-of-fit analyses of the data (29). Each of the following covariates is a binary indicator.

- 1. Inhibition of FGF signaling by bone marrow biopsy at 4 weeks.
- 2. Modulation of the bone markers (a) urinary NTX and (b) bone specific alkaline phosphatase
- 3. Baseline signature of FGF signaling in temrs of FGF R-1, FGF R-3 and FGF 9.

Time of disease progression if defined by PSA alone is defined as follows: Three consecutive PSA elevations above nadir or baseline are required. Each increment in PSA should be a minimum of 1 ng/ml and at least 2 weeks apart or will not count. The time of PSA progression will be taken as the time of the first of these PSA elevations that represents an increment by at least 25% above the nadir or baseline. Given that increments in PSA do not always represent treatment failure, particularly when novel agents with uncertain effects on PSA levels are being evaluated, clinical and radiological correlation is recommended at the discretion of the treating physician. In patients with PSA progression alone without clinical or radiological evidence of disease progression, continued therapy on study is at the discretion of the treating physician in consultation with the principal investigator.

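### The on-treatment marrow biopsy and biomarker bloods are not timed to the last dose, so they can be taken up to 72 h off drug and inhibition of FGF signaling can be missed

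*Combined protocol and SAP*

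**What the plan says.** **Dosing calendar (section 5.1).** "TKI258 if given on days 1-5, 8-12, 15-19, 22-26 (5 days on/2 days off) of each cycle". Also: "The last day of a complete cycle is Day 28". Days 27 and 28 are therefore rest days.

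**Biopsy (section 7.4.5).** "A bone marrow biopsy and aspirate will be performed between 7 and 10 weeks (preferably at week 8) after beginning treatment". No dosing day, pre- or post-dose condition, or interval from the last dose is given.

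**Bloods (section 7.4.1).** "Blood for Biomarker studies (Day 1 of Cycles 2 and 3 only" (the bracket closes there). Pre- or post-dose is not stated. Section 7.4 allows a "standing window of allowance that is equal to +/- 3 days for any laboratory testing", whereas section 7.0 gives 2 days either way. Section 7.4.2 adds that the Cycle 1 Day 26 visit may end up on the same day as the Cycle 2 Day 1 visit.

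**Duration of inhibition.** Section 1.3: "Inhibition was observed up to 24 hours (h) in some models". Section 1.4: "Target inhibition was observed for as long as 24 h after a single high dose of TKI258". Section 1.5 also gives 24 h after a single high dose. All three are nonclinical.

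**Use in the analysis (section 10.0).** "Inhibition of FGF signaling by bone marrow biopsy" is a binary covariate for PSA response (logistic regression) and for survival (Cox model). Section 10.0 dates it at 4 weeks, both in its opening text and in the covariate list. The synopsis dates it at 8 weeks.

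**Contrast.** Table 7.1 marks ECGs as pre-dose or six hours post-dose, and section 7.4.2 places a trough drug level on Cycle 2 Day 12.

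**The concern.** The biopsy is meant to show whether the drug inhibits FGF signaling in marrow, and that reading becomes a yes/no covariate for both primary outcomes. On an intermittent schedule the reading may depend on how long ago the last dose was taken. The plan times the ECGs and the drug level to dosing but leaves the pharmacodynamic samples free. The nominal blood day, and one natural reading of the preferred biopsy time, fall on the first dosing day after a rest.

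If signaling recovers during the rest, a patient whose pathway was inhibited on drug could be classed as not inhibited because of the day chosen for the procedure. That would blunt or distort the estimated association with PSA response and survival. A null association could then not be read as lack of target engagement. With 40 patients planned there is little room for such misclassification.

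**Working it through.** **1. Reproduce the plan's calendar.** Count study days from the first dose (day 1) and assume no interruptions and the same clock time each day. Day d is a dosing day if (d − 1) mod 7 < 5. For d = 1 to 28 this gives 1-5, 8-12, 15-19 and 22-26, as in section 5.1.

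**2. Nominal days.** Pre-dose gap = 24 h × (sampling day − last earlier dosing day).

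- Cycle 2 Day 1 = 28 + 1 = day 29; last dose day 26; gap 24 × 3 = 72 h.
- Cycle 3 Day 1 = 56 + 1 = day 57; last dose day 54; gap 24 × 3 = 72 h.
- Eight elapsed weeks = 1 + 56 = day 57, the same 72 h. Four elapsed weeks (section 10.0) = 1 + 28 = day 29, also 72 h.
- If taken after that day's dose, each of these gaps is under 24 h.

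**3. The biopsy window.** Seven elapsed weeks = 1 + 49 = day 50; ten = 1 + 70 = day 71. That is 71 − 50 + 1 = 22 days: 16 dosing days and 6 rest days (55, 56, 62, 63, 69, 70).

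| Gap from last dose | Dosing-day samples taken pre-dose | Dosing-day samples taken post-dose |
|---|---|---|
| under 24 h | 0 | 16 |
| 24 h | 15 | 3 (days 55, 62, 69) |
| 48 h | 3 (days 56, 63, 70) | 3 (days 56, 63, 70) |
| 72 h | 4 (days 50, 57, 64, 71) | 0 |
| **Over 24 h** | **7/22 = 32%** | **3/22 = 14%** |

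**4. Other readings of the timing.** If the preferred week 8 means days 50-56, five of the seven are dosing days; pre-dose, day 50 gives 72 h, day 56 gives 48 h and the other five give 24 h. If weeks 7 to 10 means days 43-70, there are 28 days (20 dosing, 8 rest), with 4 at 72 h and 4 at 48 h pre-dose: 8/28 = 29%.

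**5. Bloods within the laboratory window.** Three days either side of day 57 is days 54-60. The pre-dose gaps are 24, 24, 48, 72, 24, 24 and 24 h. Samples with the same visit label can differ from 24 to 72 h.

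**6. Against the documented duration.** The documents go no further than 24 h for inhibition and give no human half-life. Section 1.4 gives about 3 h in animals. As an assumed range, plasma drug left = 2^(−hours/half-life):

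| Assumed half-life | Left at 24 h | Left at 72 h |
|---|---|---|
| 3 h | 0.4% | <0.0001% |
| 12 h | 25% | 1.6% |
| 24 h | 50% | 12.5% |

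This concerns plasma drug level, not inhibition in marrow.

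**7. After the change.** The 2nd to 5th dosing days in the window are 51-54, 58-61 and 65-68, which is 12 of 22 days. On each, the gap is 24 h pre-dose and less after the dose.

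**The case against.** A reader might infer that these samples do fall 72 h after the last dose, and that the pathway will have recovered by then. The documents support neither.

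- **The biopsy is not fixed to the end of the rest.** Sixteen of the 22 window days are dosing days, and only four can reach 72 h.
- **The 72 h gap needs pre-dose sampling.** Table 7.1 writes pre-dose where it is wanted; sections 7.4.1 and 7.4.5 do not. A Day 1 sample could follow that day's dose by hours.
- **The bloods can move.** The laboratory window and the possible merging of the Day 26 and Day 1 visits can put them on other dosing days.
- **Twenty-four hours is an observed duration, not a recovery time.** It comes from single doses in nonclinical models.
- **There is evidence the other way.** Section 1.5.5 reports murine tumor concentrations up to 200-fold above plasma or normal tissue 48 h after dosing stopped.
- **Not every endpoint is time-sensitive in this way.** FGF R expression, FGF9 and mRNA have no stated time course, and the covariate analysis is exploratory.

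These points limit the claim to what can happen. They do not supply a sampling rule, and movable visits make the interval more variable. The retention evidence is a drug level at 48 h, not inhibition at 72 h. The same section says normal-tissue levels fall rapidly, while section 3.1 covers host as well as tumor cells and about 60% of biopsies are expected to be positive (0.6 × 40 = 24 patients). Section 1.3 also reports no accumulation on day 15 at 500 and 600 mg on this schedule, though that too concerns exposure.

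**Conclusion.** The point holds as a gap in sampling control. The nominal Day 1 bloods, and a biopsy at exactly eight elapsed weeks, can be 72 h from the last dose. Over the biopsy window, 14% to 32% of calendar days exceed 24 h, depending on whether dosing-day samples follow or precede the dose. These are shares of days, not of patients; the documents do not say how biopsies will spread over the window.

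Inhibition of signaling can therefore be missed, and the binary covariate can depend on the day of sampling. Whether it would be missed in patients is not established, because no document gives a recovery time at 48 or 72 h. The argument applies to signaling inhibition and cannot be extended to the expression and mRNA endpoints. This is a cheap improvement, held with moderate confidence.

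**What to change.** 1. **Section 7.4.5.** Keep the 7-10 week window, but schedule the biopsy on the 2nd to 5th consecutive dosing day of a week. Cycle 2 Day 26 (day 54) qualifies and is already an ECG time point in Table 7.1.
2. **Section 7.4.1.** Move the biomarker bloods from Day 1 of Cycles 2 and 3 to Day 26 of Cycles 1 and 2, both existing time points. For these draws, confine the laboratory window to Days 23-26 and do not let a merged visit shift them to Day 1; otherwise 3 days either side of Day 26 would reach Day 29 and restore the 72 h gap. Reconcile the differing windows in sections 7.0 and 7.4.
3. **Case report form.** Record the time since last dose for every biopsy and biomarker blood.
4. **Section 10.0.** Keep samples taken more than 24 h after a dose in the main correlative analysis, and prespecify a sensitivity analysis that leaves them out. Dropping them outright would shrink an already small biopsy set.
5. **Synopsis and section 10.0.** Reconcile 8 weeks with 4 weeks for the biopsy covariate. The on-treatment biopsy in section 7.4.5 starts at week 7, so it cannot supply a 4-week reading.

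Cost: wording changes, one extra data field and a narrower choice of biopsy days (12 of 22). No added biopsy, draw or visit, and no change to dosing is proposed.

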8.0 WITHDRAWAL FROM STUDY TREATMENT

The investigator may withdraw a patient from study treatment phase for any of the following reasons:

- Dosing noncompliance: Study drug administration and dosing compliance will be assessed on Week 4 visit. A count of study drug will be conducted during this visit and patient dosing compliance will be assessed. If dosing compliance is not 100% in the absence of toxicity, patient should be re-instructed regarding proper dosing procedures and continue in the study. Subsequent dosing compliance procedure will be conducted at each study visit. If a patient misses 14 or more doses within a single 28-day cycle, the patient should be discontinued from the study treatment phase. All End-of-Study treatment procedures should be followed. The patient will be followed for survival.
- Sustained Side Effects: Patients who have sustained toxicities, such as described in 6.5.6, which does not return to NCI CTCAE (version 3.0) Grade 1 or less with appropriate medical management, should be discontinued from the study treatment phase. All End-of-Study treatment procedures should be conducted. The patient will be followed for survival.
- Initiation of new anticancer treatment: Patients will be discontinued from the study treatment when investigator, in his or her judgment, determines new treatment for

prostate cancer is warranted. All End-of-Study treatment procedures should be conducted and the patient will be followed for survival.

- Administration of prohibited medications: The patient will be discontinued from the protocol treatment when prohibited drug is administered. All End of Study treatment procedures should be conducted. The patient will be followed for survival. Supportive care medications are permitted with their use following institutional guidelines. For patients who did not undergo orchiectomy, concurrent treatment with LHRH analogue is mandatory and must be recorded. The concurrent administration of other anti-cancer therapy, including cytotoxic, hormonal (except LHRH agonists), or immunotherapy is prohibited during study treatment phase. Use of other investigational drug therapy for any reason is prohibited
- Patient's withdraws consent. In this event, the reason(s) for withdrawal must be documented A patient's decision to take part in the study is voluntary and he may choose not to take part in the study or to stop taking part at anytime. If he chooses not to take part or to stop at anytime, it will not affect his future medical care or medical benefits.

